7.2. Number of Patients and Sites

Approximately 700 patients are planned to be randomized in the study at approximately 70 study centers.

7.3. Method of Treatment Assignment and Blinding

Patients will be randomized in a 3:5:2 ratio (12 mg BID:8 mg BID:placebo). Randomization will be stratified by scalp hair loss into one of the following two categories: 1) Partial scalp hair loss (SALT ≥ 50 and < 95); 2) Complete or near-complete scalp hair loss (SALT ≥ 95). The randomization schedule will be generated prior to study start.

All study patients, Investigators, and site study staff will be blinded to study drug assignment for the duration of the study. Tablets and packaging of CTP-543 and placebo will be identical in appearance.

7.4. Rationale for Study Design, Doses, and Primary Endpoint

Double-blind, randomized, placebo-controlled studies are considered optimal for obtaining unbiased estimates of the efficacy and safety of investigational products. The Severity of Alopecia Tool (SALT) (Olsen, 2004) was introduced as part of investigative guidelines published by the National Alopecia Areata Foundation is widely used to assess the extent of the scalp surface hair loss in AA. The SALT has been used as the hair loss measurement scale in all the studies of CTP-543 in patients with alopecia areata to date. The 24-week duration of the Treatment Period has been shown to be sufficient in establishing hair regrowth with CTP-543 and to significantly differentiate active doses from placebo as well as differentiate between doses of CTP-543.

The selection of the 8 mg and 12 mg BID doses of CTP-543 for this study is supported by the efficacy and safety of CTP-543 observed in the completed and analyzed Phase 2 CP543.2001, CP543.2002, and CP543.2003 studies. Analysis of the primary efficacy endpoint in CP543.2001 showed that the proportions of responders (patients achieving at least a 50% relative reduction in SALT score from Baseline at Week 24) were significantly greater in the 8 mg BID group and 12 mg BID group compared with the placebo group ($P < 0.001$ for both) and compared with the 4 mg BID group ($P = 0.030$ and $P = 0.003$, respectively). For the analysis performed on the efficacy population, 9.3% of patients in the placebo group and 21.4% of patients in the 4 mg BID

group were responders, compared with 47.4% in the 8 mg BID group and 58.3% in the 12 mg BID group. Results also showed a significantly greater proportion of responders in the 8 mg BID and 12 mg BID groups which had at least 50%, 75%, and 90% relative reduction in SALT score by Week 24 compared with both the placebo group and the 4 mg BID group.

Additionally, both the 8 mg BID group and the 12 mg BID group had significantly greater proportions of patients who achieved an absolute SALT score ≤ 20 at Week 24 compared with the placebo group. Achieving a SALT score ≤ 20 has been reported by AA patients and clinicians to represent clinically-meaningful treatment success for AA ([Wyrwich, 2020](#)). In the Wyrwich study, qualitative interviews were conducted in the US with hair expert dermatologists and AA patients who had experienced $\geq 50\%$ scalp hair loss. The clinicians judged that 80% scalp hair represented treatment success. Adult and adolescent AA patients participating in the study perceived that, short of 100% scalp hair, the presence of $\sim 70\text{-}90\%$ scalp hair (median 80%) represented treatment success. Nearly all queried clinicians and patients in this study agreed that for patients with $\geq 50\%$ scalp hair loss, successful treatment would be hair regrowth resulting in $\leq 20\%$ scalp hair loss.

Therefore, based on the efficacy and safety data observed in the CP543.2001, CP543.2002, and CP543.2003 studies, 8 mg BID and 12 mg BID of CTP-543 will be assessed further for efficacy and safety in the Phase 3 program in patients with moderate to severe alopecia areata. This Phase 3 study will employ SALT as the hair loss assessment tool and the primary efficacy endpoint will be the percentage of patients who achieve a SALT score ≤ 20 , as this represents a clinically-meaningful treatment success for patients with AA.

Table 2: Schedule of Assessments

Event ¹	Screening	Baseline/ Randomization	Treatment Period ⁴				Safety Follow-Up
	Day -28 to Day -1 ² (Visit 1)	Day 1 ³ (Visit 2)	Week 2 (Visit 3)	Week 4, 8, 12 (Visit 4, 5, 6)	Week 16, 20 (Visit 7, 8)	Week 24 (Visit 9)/ ET Visit	Week 28 (Visit 10) ⁵
Informed consent	X						
Eligibility assessment	X	X					
Demographics	X						
Medical history	X	X					
Randomization		X					
Complete physical examination	X	X				X	X
Brief physical examination				X	X		
Height	X						
Weight	X	X		X	X	X	X
Pregnancy test ⁶	X	X		X	X	X	X
Tuberculosis test	X						
Clinical laboratory testing ^{7,8}	X ⁹	X	X ¹⁰	X	X	X	X
HBV and HCV test	X						
12-lead electrocardiogram	X			X ¹²		X	
Vital signs	X	X		X	X	X	X
Severity of Alopecia Tool assessment ¹¹	X	X		X	X	X	
Photographs of the scalp	X	X		X	X	X	
Photographs of eyebrows, eyelashes, and hands		X		X ¹²		X	
Eyebrow Assessment (BETA)		X		X ¹²		X	
Eyelash Assessment (BELA)		X		X ¹²		X	
Patient Reported Outcome Scales: SPRO and QPRO		X		X ¹²	X	X	
Patient and Clinical Global Impression of Improvement (PGI-I, CGI-I ¹¹)				X ¹²	X	X	
Patient and Clinical Global Impression of Severity (PGI-S, CGI-S ¹¹)		X		X ¹²	X	X	
Hospital Anxiety and Depression Scale (HADS)		X				X	
Dispense study drug ¹³		X		X	X		
Study drug accountability				X	X	X	
Adverse events ¹⁴	X	X	X	X	X	X	X
Concomitant medications ¹⁴	X	X	X	X	X	X	X

HBV = hepatitis B virus; HCV = hepatitis C virus
 
¹ Due to the COVID-19 pandemic, patient study visits may be performed remotely when the provider and patient are not able to be physically present in the clinic. Study personnel should strive to perform assessments per the schedule of events above with the understanding that all assessments may not be able to be performed (ECGs, vitals, SALT assessments).
 
² Randomization/Day 1 may occur any time after eligibility has been confirmed.
 
³ All subsequent visits and week increments should be based on the date of Visit 2 (Day 1).
 
⁴ All visit windows are ± 2 days.
 
⁵ The Safety Follow-Up Visit is intended for those patients who do not roll over into the Open-Label Extension.
	
⁶ Serum pregnancy test only for females of childbearing potential
 
⁷ Includes hematology, serum chemistry, and lipids (fasted) performed by the central lab.
 
⁸ Collected pre-dose.
 
⁹ Will include thyroid stimulating hormone and hemoglobin A1c at Screening only.
 
¹⁰ Will include hematology and serum chemistry only.
 
¹¹ Should be performed by the same rater for the patient for the duration of the study.
 
¹² Performed at Week 12 only.
 
¹³ Due to COVID-19, Direct to Patient (DTP) shipping services may be warranted in cases where a patient is not able to attend in clinic visits or a site is closed.
 
¹⁴ Collection is ongoing.

---	---

8. SELECTION AND WITHDRAWAL OF PATIENTS

Patients eligible for enrollment in the study must meet all of the following inclusion criteria and none of the exclusion criteria.

8.1. Patient Inclusion Criteria

1. Written informed consent, and authorization for release and use of protected health information.
2. Between 18 and 65 years of age, inclusive, at the time of informed consent.
3. Definitive diagnosis of alopecia areata with a current episode of scalp hair loss lasting at least 6 months and not exceeding 10 years at the time of Screening. Total disease duration greater than 10 years is permitted.
4. At least 50% scalp hair loss, as defined by a SALT score ≥ 50 , at Screening and Baseline.
5. Female subjects are eligible to participate if at least one of the following conditions applies:
 - a) Is a woman of childbearing potential (WOCBP) and using a medically highly effective form of birth control with a failure rate less than 1% per year from at least 4 weeks prior to Baseline until at least 30 days following last dose of study drug. Examples of medically highly effective birth control methods include:
 - i. Combined (estrogen and progestogen containing) hormonal contraception (oral, patch, vaginal ring)
 - ii. Progestogen-only hormonal contraception associated with inhibition of ovulation (oral, injectable, implantable)
 - iii. Intrauterine device or intrauterine hormone-releasing system
 - iv. Bilateral tubal occlusion
 - v. Vasectomized partner or partner of the same sex
 - vi. Double barrier method (any combination of physical and chemical methods)
 - b) Is not a WOCBP:
 - i. Premenopausal with one of the following:
 - a. Documented hysterectomy;
 - b. Documented bilateral salpingectomy;
 - c. Documented bilateral oophorectomy.
 - ii. Postmenopausal (cessation of menses for at least 12 months prior to screening)
Postmenopausal is defined as no menses for at least 12 months prior to screening without an alternative medical cause.
6. Male participants must:
 - a. Agree to use, with their partners, one of the highly effective contraceptive methods listed in Inclusion Criterion 5, from Baseline until at least 30 days following last dose of study drug.
 - b. Refrain from donating sperm during the study and for at least 30 days after the end of the study.
7. Willing to comply with the study visits and requirements of the study protocol.

8.2. Patient Exclusion Criteria

1. History or presence of hair transplants.
2. Treatment with other medications or agents within 1 month of Baseline or during the study that may affect hair regrowth or immune response, including but not limited to: corticosteroids administered orally, intravenously or intramuscularly, or applied to areas of skin affected by alopecia (intranasal and inhaled corticosteroids are allowed, eye and ear drops containing corticosteroids are also allowed); oral retinoids, oral cyclines (minocin, tetracycline); platelet-rich plasma injections; topical application to affected areas of retinoids, anthralin, squaric acid, diphenylcyclopropenone, or minoxidil.
3. Treatment with systemic immunosuppressive medications including but not limited to methotrexate, cyclosporine, azathioprine, chloroquine derivatives, etanercept, JAK inhibitors within 3 months of Screening or during the study.

NOTE: Patients previously treated with a Janus Kinase inhibitor more than 3 months prior to Screening may be allowed to enter the study at the discretion of the PI, if their previous treatment with a JAK inhibitor was well tolerated, and subsequent JAK treatment would not be thought to put the subject at risk. Consultation with the Medical Monitor may be warranted should questions arise with regard to prior tolerability.

4. Treatment with biologics (e.g., adalimumab, atlizumab, canakinumab, certolizumab, fontolizumab, golimumab, infliximab, mepolizumab, rituximab, secukinumab, tocilizumab, ustekinumab) within 6 months of Screening or during the study.
5. Active scalp inflammation, psoriasis, or seborrheic dermatitis requiring topical treatment to the scalp, significant trauma to the scalp, or other scalp condition that may interfere with the SALT assessment, or untreated actinic keratosis anywhere on the body at Screening and/or Baseline.
6. Known history of moderate to severe androgenic alopecia or female pattern hair loss prior to alopecia areata.
7. Unwilling to maintain a consistent hair style, including shampoo and hair products (including hair dye, process, and timing to hair appointments), and to refrain from weaves or extensions throughout the course of the study, or shaving of scalp hair for 2 weeks preceding a SALT assessment.
8. Use of adhesive wigs, other than banded perimeter wigs, during the study.
9. History of a lymphoproliferative disease or malignancy, other than non-melanoma skin cancer or cervical carcinoma. Patients with 3 or more basal or squamous cell carcinomas diagnosed in the past 2 years are excluded.
10. History of solid organ or hematological transplantation.
11. Fever, inflammation, or systemic signs of illness suggestive of systemic or invasive infection or a positive SARS-CoV-2 test result within 2 weeks prior to Baseline.
12. Abnormal levels of thyroid stimulating hormone at Screening, defined as <0.9 x the lower limit of normal (LLN) and >1.5 x the upper limit of normal (ULN).

13. Screening labs outside the normal range for parameters associated with potential risk for treatment under investigation. This will include but is not limited to:
 - a) Platelets $\leq 100 \times 10^9/L$ or $\geq 600 \times 10^9/L$
 - b) Absolute neutrophil count $\leq 1.5 \times 10^9/L$
 - c) Hemoglobin levels ≤ 10.5 g/dL for females, or hemoglobin levels ≤ 12.0 g/dL for males
14. Screening blood level of hemoglobin A1c $\geq 7.5\%$ (58 mmol/mol, 9.3 mmol/L).
15. Abnormal liver function at Screening, defined as $\geq 2 \times$ ULN of serum alanine transaminase, serum aspartate transaminase, and serum alkaline phosphatase, or $\geq 1.5 \times$ ULN total bilirubin (unless isolated Gilbert's syndrome).
16. Abnormal renal function (estimated glomerular filtration rate < 60 mL/min/1.73 m² using the CKD-EPI 2009 equation) at Screening.
17. Patient has positive results for hepatitis B surface antigens (HBsAg), antibodies to hepatitis B core antigens (anti-HBc), or hepatitis C virus (HCV) at Screening, or known history of human immunodeficiency virus infection. Subjects who test positive for HCV but who are in remission (sustained virologic response as evidenced by undetectable HCV RNA level using a sensitive assay ≥ 12 weeks after completion of HCV therapy) are allowed inclusion in the study.
18. Vaccination with a live attenuated vaccine during the study or up to 6 weeks prior to randomization.
19. History of previous active disease due to *M. tuberculosis* (TB) without documentation of successful treatment; OR, patient has a positive result from a Tuberculin Skin Test (TST) or a QuantiFERON-TB Gold (QFT) test performed at Screening.

NOTE: If the patient has a positive QFT result at Screening and: (1) has no history of successful treatment for either active disease or latent infection due to *M. tuberculosis*, or (2) currently resides in an area with low prevalence of tuberculosis, or (3) has no lifetime history of occupational or household exposure to person(s) with tuberculosis, then the initial Screening QFT result may be a false-positive. In this instance, a second Screening test for latent TB infection should be obtained – either: (1) a repeat QFT test or (2) a Tuberculin Skin Test (TST). The repeat QFT test must be negative or the TST should show < 15 mm induration (considered negative TST) before being considered eligible for the study.
20. History of prolonged QT syndrome or a Screening QTc interval with Fridericia's correction (QTcF) > 450 msec for males or QTcF > 470 msec for females.
21. History of alcohol, medication, or illicit drug abuse within 1 year before the first dose of study drug.
22. Females who are nursing, pregnant, or planning to become pregnant while in the study, and for 30 days after last dose of study drug.
23. Participation in another investigational study within the greater of 4 weeks or 5 half-lives of an investigational medication prior to screening or during the study.

24. Use of strong cytochrome P450 3A4 (CYP3A4) inhibitors (such as, but not limited to clarithromycin, conivaptan, grapefruit juice, indinavir, itraconazole, ketoconazole, lopinavir/ritonavir, mibefradil, nefazodone, nelfinavir, posaconazole, saquinavir, telaprevir, telithromycin, voriconazole, or fluconazole) dosed for systemic exposure.
25. Use of strong CYP3A4 inducers (such as, but not limited to barbiturates, carbamazepine, efavirenz, glucocorticoids, modafinil, nevirapine, oxcarbazepine, phenobarbital, phenytoin, pioglitazone, rifabutin, rifampin, St. John's Wort, or troglitazone) dosed for systemic exposure.
26. Donation of blood > 499 mL of blood or plasma within 56 days of Screening (during a clinical trial or at a blood bank donation) and for 30 days after last dose of study drug.
27. Clinically significant medical condition, psychiatric disease, or social condition, as determined by the Investigator, that may unfavorably alter the risk-benefit of study participation, adversely affect study compliance, or confound interpretation of study results.

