10. STUDY ASSESSMENTS AND PROCEDURES

The schedule of assessments and procedures is presented in [Table 2](#) and should be referenced for details regarding the collection of each assessment at each visit. Due to the COVID-19 pandemic, patient safety and some other assessments outlined below may be performed remotely if travel restrictions, quarantine, and/or site closures are presented and the Principal Investigator and the patient are not able to be physically present in the clinic.

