10.12. Clinical Laboratory Assessments

Clinical laboratory assessments are presented in Section 17.1. Clinical laboratory samples should be collected at the beginning of each clinic visit and just prior to a dose on all Study Visit Days and will be processed by a central laboratory. In the event a patient is unable to attend an in-clinic visit due to COVID-19, clinical laboratory blood draws may be performed by a Home Health Care agency or a local laboratory. Patients should try to have laboratory blood draws performed in the morning and dose study drug after clinical laboratory blood draws are completed.

The results of clinical laboratory tests conducted at the Screening Visit (and prior to dosing) must be assessed by the Investigator to determine each patient's eligibility for participation in the study. The Investigator should indicate review of the laboratory reports throughout the study by signing and dating each report.

All clinical laboratory results that fall outside the reference range will be interpreted by the Investigator as Abnormal, not clinically significant, or Abnormal, clinically significant. Laboratory results deemed Abnormal, clinically significant will be recorded as an adverse event in the eCRF (see additional criteria outlined in Section 11.1). Clinically significant laboratory abnormalities indicative of hematologic or other effects requiring intervention should be discussed with the Medical Monitor(s). Additional tests and evaluations required to establish the significance or etiology of a clinically significant abnormal result or to monitor the course of an adverse event should be obtained when clinically indicated. Whenever possible, the etiology of the clinically significant abnormal findings will be documented on the eCRF.

10.13. **Unscheduled Visit**

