17. APPENDICES

17.1. Clinical Laboratory Assessments

Hematology	Chemistry	Serum Pregnancy
Complete blood count Absolute neutrophil count Absolute eosinophil count Platelet count White blood cell count with differential Absolute reticulocyte count Hemoglobin A1c	Alanine aminotransaminase Albumin Alkaline phosphatase Amylase Aspartate aminotransaminase Total bilirubin Direct bilirubin Indirect bilirubin Blood urea nitrogen C-Reactive Protein (CRP) Calcium Carbon dioxide Chloride Creatinine Creatine kinase Glucose Lipase Total protein Phosphorus Potassium Sodium Uric Acid	Human chorionic gonadotropin (females of childbearing potential only)
Serology	Lipids (Fasted)	Other
Hepatitis B Surface Antigen (HBsAg) Hepatitis C Virus Antibodies (HCV Ab)	Total cholesterol Low-density lipoprotein High-density lipoprotein Triglycerides	Tuberculosis Thyroid stimulating hormone

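### Exclusion 12 joins its two TSH limits with *and* where *or* is meant, and exclusion 17 relies on an anti-HBc result that the itemised serology list does not name (minor).

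*Protocol*

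**What the plan says.** **TSH.** Exclusion 12 in Protocol Section 8.2 removes patients with abnormal thyroid stimulating hormone at Screening, "defined as <0.9 x the lower limit of normal (LLN) and >1.5 x the upper limit of normal (ULN"). The synopsis has the same wording. Table 2, footnote 9, puts the TSH measurement at Screening only. The next item in the list, 13a, also sets a lower and an upper limit but joins them differently: "Platelets $\leq 100 \times 10^9/L$ or $\geq 600 \times 10^9/L".

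**Hepatitis serology.** Exclusion 17, in Section 8.2 and the synopsis, lists as grounds for exclusion positive results for HBsAg, "antibodies to hepatitis B core antigens (anti-HBc), or hepatitis C virus (HCV) at Screening". Three places describe the tests:

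- Section 10.12 sends the reader to the appendix: "Clinical laboratory assessments are presented in Section 17.1". The serology entry there reads "Hepatitis B Surface Antigen (HBsAg) Hepatitis C Virus Antibodies (HCV Ab"). Under its Other heading the appendix also gives "Tuberculosis Thyroid stimulating hormone".
- Section 10 says that Table 2 "should be referenced for details regarding the collection of each assessment at each visit".
- The relevant Table 2 row reads "HBV and HCV test", marked at Screening. SAP Appendix 15.2 repeats it unchanged.

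**The concern.** Both items decide who may be randomized, so their wording has to work as a rule.

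If item 12 is applied word for word, it never operates. A patient with a TSH well outside the range then complies with the text but breaks its evident intent. That leaves room for inconsistent handling when deviations are classified before database lock (SAP Section 7.1), and major deviations remove a patient from the Per Protocol Population (SAP Section 5).

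Item 17 needs a result before it can be applied. Under Protocol Section 14.6, each site must hold source confirmation that the patient meets the eligibility criteria. If a laboratory panel were built from Appendix 17.1 alone, there would be no anti-HBc result to confirm.

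**Working it through.** The plan states no figure on this point, so there is none to reproduce. The check is one inequality and one comparison of sections.

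**TSH**

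1. Inputs: the two limits in exclusion 12, 0.9 × LLN and 1.5 × ULN, and one Screening TSH value, x. The only assumption is that the reference range is ordered, 0 < LLN < ULN.
2. Literal rule: exclude if x < 0.9 × LLN and x > 1.5 × ULN.
3. Gap between the limits: 1.5 × ULN − 0.9 × LLN > 1.5 × LLN − 0.9 × LLN = 0.6 × LLN > 0.
4. The upper limit therefore always lies above the lower one, and no x satisfies both conditions. The literal exclusion set is empty for every reference range.
5. Numerical check: over 200,000 random combinations of LLN, ULN and x, 0 met the literal rule. The algebra already settles the matter.
6. With *or*, the rule excludes x < 0.9 × LLN and also excludes x > 1.5 × ULN. This is the only reading under which the limits do any work.

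Nothing elsewhere in the protocol or SAP restates or corrects the TSH limits.

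**Anti-HBc**

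| Place | Hepatitis markers named |
|---|---|
| Section 8.2 and synopsis, item 17 | HBsAg, anti-HBc, HCV |
| Appendix 17.1, serology | HBsAg, HCV antibodies |
| Table 2 and SAP Appendix 15.2 | HBV and HCV, no marker given |

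1. Item 17 names two hepatitis B markers and the appendix names one.
2. The appendix does use shorthand. Hemoglobin comes within the complete blood count, and eGFR is calculated from creatinine. Anti-HBc cannot be supplied in that way, because an antigen test does not yield an antibody result.
3. The Table 2 row is broad enough to include anti-HBc but does not say so.
4. The test is therefore implied by item 17, permitted by Table 2, and missing from the one list that itemises serology.

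**The case against.** **Item 12 is clear enough.** It speaks of abnormal levels in the plural, and the two ranges can be read as a list of what counts as abnormal. Item 15 also joins its liver enzymes with *and*, so this may be a drafting habit. That stands as an account of intent, and sites most likely apply *or*. It does not rescue the wording of a definition applied to a single value, especially when item 13a handles the same situation correctly.

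**Anti-HBc is already required.** Item 17 makes it exclusionary, patients must meet no exclusion criterion, the Investigator must assess Screening results for eligibility (Section 10.12), and Table 2 has a hepatitis row separate from routine laboratory testing. A laboratory manual outside these documents may list the marker. Much of this stands, and it is why the point is small. Investigator review cannot, however, cover a result that was not ordered.

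**The appendix is not an inventory.** It also lacks HCV RNA, which item 17's remission exception needs, and a SARS-CoV-2 test, which item 11 refers to. This stands: a missing entry is weak evidence about what was actually run.

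**Other safeguards exist.** Item 13 is open-ended on Screening laboratory values, and item 27 allows investigator judgement. They reduce the practical risk, but neither supplies a TSH limit or a hepatitis B marker.

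**It may be late.** The synopsis estimates the last visit for February 2022, and SAP Section 13 reports that reasons for missing data had already been reviewed blind. Enrolment may have finished by then, although the documents do not say so. If it had, the correction would serve mainly the record and deviation classification.

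**Stronger readings.** A reader might infer that patients with thyroid disease or past hepatitis B infection were enrolled, or that anti-HBc was never measured. The documents support neither. They contain no screening results, no prevalence figures and no laboratory manual.

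**Conclusion.** Minor, and wrong as written in both parts.

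- **TSH:** no value meets exclusion 12 on its literal terms. This rests only on LLN being below ULN. The intended rule is not in doubt.
- **Anti-HBc:** one of the two hepatitis B markers in exclusion 17 is absent from the Appendix 17.1 serology list, and the generic Table 2 row leaves open whether it is run. This is an inconsistency between sections, not evidence of a missed test.

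No number of affected patients can be given. The documents state no safety reason for the TSH rule, and none is claimed here. There is no effect on power, alpha or the primary analysis, which uses the Efficacy Population. Any effect through deviation classification reaches only the Per Protocol analysis, which SAP Section 8.2.2 treats as supportive. This belongs in the lowest tier of comments.

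**What to change.** 1. In exclusion 12, change *and* to *or* between the two TSH limits, in Section 8.2 and in the synopsis.
2. Add anti-HBc to the serology list in Appendix 17.1.
3. In the hepatitis row of Table 2, name HBsAg, anti-HBc and HCV. Match this in SAP Appendix 15.2 if that is reissued.

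No threshold, visit, sample size or analysis changes. The cost is a short protocol amendment. Under Section 13.4, sites must wait for IRB/EC approval unless the amendment is administrative, and there are approximately 70 centers, so it is best folded into the next planned amendment. If the laboratory already runs anti-HBc, only the documents change; otherwise one assay is added to a Screening sample. Any site that had read item 12 literally would have narrower eligibility from that point.

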1. SYNOPSIS

Name of Sponsor/Company: Concert Pharmaceuticals, Inc.	
Name of Investigational Product: CTP-543	
Name of Active Ingredient: Deuterated ruxolitinib	
Title of Study: A Double-Blind, Randomized, Placebo-Controlled Study to Evaluate the Efficacy and Safety of CTP-543 in Adult Patients with Moderate to Severe Alopecia Areata	
Study center(s): Multicenter study; approximately 70 sites (North America and European Union)	
Studied period (years): Estimated date first patient first visit: October 2020 Estimated date last subject last visit: February 2022	Phase of development: 3

Objectives:
 
The overall objectives of the study are to assess the efficacy and safety following administration of CTP-543 in adult patients with moderate to severe alopecia areata.
 
The primary objectives of the study are to assess:
 
 • The efficacy of CTP-543 on regrowth of hair following 24 weeks of treatment • The safety of CTP-543 following 24 weeks of treatment. 
The secondary objectives of the study are to assess:
 
 • Clinician- and patient-reported impression of the severity and improvement of alopecia areata • Patient-reported satisfaction with their scalp hair • Patient-reported levels of anxiety and depression • Changes in eyebrows and eyelashes. 	

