10.1. Demographic Characteristics and Medical History

Demographic characteristics [i.e., sex, ethnic origin, date of birth (as appropriate per local regulations), and calculated body mass index] will be collected at the Screening Visit, between Day -28 and -1, and detailed on the eCRF.

The patient's alopecia areata will be classified by scalp hair loss into one of two categories defined for this study:

- 1) Partial scalp hair loss ($SALT \geq 50$ and < 95);
- 2) Complete or near-complete scalp hair loss ($SALT \geq 95$).

Key criteria that distinguish alopecia areata from other forms of hair loss may include abrupt onset of disease, a history of recurrence and spontaneous remission, response to topical or intralesional steroid treatment, and distribution of hair loss pattern. Care must be taken during the evaluation to assess for other causes of hair loss such as trichotillomania, or scarring alopecia and other forms of non-scarring alopecia. Evidence of thinning hair should be distinguished from pattern hair loss or telogen effluvium and evidence of inflammation should be investigated to rule out infection, as appropriate.

Thorough medical history, including current medications and any prior janus kinase (JAK) inhibitor use, nail and facial hair involvement, co-morbidities, serious infection history and exposure risk, including HIV, as well as history or vaccination against herpes zoster will be collected at the Screening Visit, and at the Randomization Visit on Day 1 for each dose group.

Medical history should be thoroughly probed for potential exposure to serious infections such as HIV, history or vaccination against herpes zoster or other recent live virus vaccinations, prior SARS-CoV-2 infection, as well as cancer risk due to the potential immunosuppressive properties and known adverse events associated with JAK inhibitors.

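### In the exclusion 19 NOTE, condition (1) alone opens the TB retest, so a known TB exposure never limits it for an untreated QFT-positive patient

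*Protocol*

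**What the plan says.** Item 19 has two limbs. The first excludes previous active TB "without documentation of successful treatment; OR, patient has a positive result" on a skin test (TST) or QFT at Screening; that positive result is the second limb.

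A NOTE then qualifies a positive QFT. The first result may be treated as a possible false positive under any one of three conditions. Condition (1) is met by a patient who "has no history of successful treatment for either active disease or latent infection due to" the TB organism. Two alternatives follow in the list, one on residence and one on contact with people who have TB: "or (2) currently resides in an area with low prevalence of tuberculosis, or (3) has no lifetime history of occupational or household exposure". When any of the three is met, one further test is obtained, either a repeat QFT or a TST. The clearing rule is: "The repeat QFT test must be negative or the TST should show < 15 mm induration (considered negative TST) before being considered eligible".

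The synopsis carries the same NOTE with the same connectors.

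**The concern.** Residence and exposure are listed as reasons to doubt a positive QFT, so one expects them to affect who is retested. Joined by *or* to condition (1), they affect no untreated patient. Condition (1) is also a weak sign of a false positive, because every patient with a true, untreated latent infection meets it.

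What is at stake is participant safety. An untreated patient with a known TB contact and a positive QFT can enter after one discordant negative test. If that second result is the wrong one, a latent infection goes untreated into up to 24 weeks of study drug. Section 10.1 asks for infection history to be probed, "as well as cancer risk due to the potential immunosuppressive properties and known adverse events associated with JAK inhibitors". Table 2 marks the TB test at Screening only, so no later scheduled test would reveal the miss.

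**Working it through.** The plan gives no figure to reproduce. The check is a truth table of the NOTE for a patient with a positive Screening QFT.

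**Inputs** (section 8.2, item 19 and its NOTE)
- U: no history of successful TB treatment, condition (1)
- L: lives in a low-prevalence area, condition (2)
- N: never exposed at home or at work, condition (3)
- Retest as written: U or L or N
- Retest under the fix: N

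| Row | U | L | N | As written | Fix |
|---|---|---|---|---|---|
| 1 | yes | yes | yes | retest | retest |
| 2 | yes | yes | no | retest | refused |
| 3 | yes | no | yes | retest | retest |
| 4 | yes | no | no | retest | refused |
| 5 | no | yes | yes | retest | retest |
| 6 | no | yes | no | retest | refused |
| 7 | no | no | yes | retest | retest |
| 8 | no | no | no | refused | refused |

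**As written**
- Untreated (rows 1–4): 4 of 4 reach the retest, so L and N change the result in 0 of 4 rows.
- Treated (rows 5–8): 3 of 4. Total 4 + 3 = 7 of 8.
- Exposed (rows 2, 4, 6, 8): 3 of 4; exposed and untreated (rows 2, 4): 2 of 2.
- Rows 4 and 8 differ only in treatment history. The successfully treated patient is refused and the untreated one is retested.

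**From retest to eligibility.** Item 19 is cleared when there is no prior active TB lacking documented successful treatment, the retest is open, and the second test is negative. For rows 2 and 4 without prior active TB, one negative second test clears the item whether or not the patient lives in a low-prevalence area. The 15 mm limit is the same for exposed and unexposed patients, so exposure does not enter at that step either. Prior active TB without documented successful treatment remains excluded in every row, as does a positive second test.

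**Under the fix**
- Untreated 2 of 4, treated 2 of 4. Total 2 + 2 = 4 of 8.
- Exposed 0 of 4; unexposed 4 of 4, as now.
- Rows changed: 7 − 4 = 3 (rows 2, 4 and 6), all exposed.

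**Other repairs, for comparison**
- Requiring all three conditions leaves only row 1 (1 of 8). It also refuses the unexposed rows 3, 5 and 7.
- For untreated patients, requiring (1) with either (2) or (3) leaves 3 of 4 and still retests the exposed patient in row 2.

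**The case against.** The strongest defence is that the three conditions grant no eligibility. They only give a reason to doubt the first result, and the second test decides. A rule that retests on any one reason for doubt is coherent. The Amendment 3 log shows that the superseded text also allowed a further test when a false positive was suspected, with no condition on residence or exposure, and that the replacement text was adopted with *or*. A broad trigger may therefore be what the sponsor wanted.

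There are other safeguards:
- Section 10.1: "serious infection history and exposure risk, including HIV, as well as history or vaccination against herpes zoster will be collected at the Screening Visit", and again on Day 1.
- Section 10.10 and Table 2: complete examinations at Screening, Day 1, Week 24 and Week 28, and brief ones at Weeks 4 to 20, look for signs of TB. Telemedicine examinations also cover exposure to TB.
- Section 10.13 provides Unscheduled Visits for suspected TB, and section 8.3 lets the investigator stop treatment at any time.
- Item 27 excludes a clinically significant condition "as determined by the Investigator, that may unfavorably alter the risk-benefit of study participation".

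Much of this stands. The second test is a real barrier, and the history and first examinations come before dosing. But none of these provisions states what a known exposure does to the retest. The quoted history sentence does not name TB, the examinations look for active disease, the telemedicine question arises only at remote visits, and item 27 is left to individual investigators at about 70 sites.

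A reader might infer that *or* is a drafting error for *and*. The documents do not show this; the Amendment 3 log has the same word. A reader might also infer that low-prevalence residence should be made binding. No harm is shown for unexposed patients living elsewhere, and the protocol does not define low prevalence.

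**Conclusion.** The point holds for known exposure. As written, household or occupational contact with TB never limits the retest for an untreated patient. Such a patient, QFT-positive and without prior active TB, clears item 19 on one negative second test. The wording should be changed.

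The size can be stated only as logic: 7 of 8 profiles reach the retest, including 3 of 4 exposed and 2 of 2 exposed and untreated. The profiles are unweighted. The documents give no number of QFT-positive, exposed or positive-then-negative patients and no error rate for the second test, so no count of affected patients is claimed.

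The conclusion rests on reading *or* in its ordinary sense. It does not depend on how many patients at the North American and EU sites would count as low-prevalence residents, since exposed untreated patients pass through condition (1) either way. It would be wrong to infer that any QFT-positive patient can enter, because a negative second test is required. The trial's efficacy conclusions are not in question either, as nothing in the analysis depends on this rule.

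**What to change.** In section 8.2 and in the synopsis, delete conditions (1) and (2) from the NOTE and keep condition (3) as the only one. A positive Screening QFT may then be regarded as a possible false positive, and a second Screening test obtained, only when the patient has never had occupational or household contact with a person with TB. Leave the second-test requirement (repeat QFT negative, or TST under 15 mm) and the first limb of item 19 as they are.

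The rule is then the same for treated and untreated patients, and sites need no definition of low prevalence.

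The cost is a wording change in two places and some screen failures. Three exposed profiles lose the retest: untreated in a low-prevalence area, untreated elsewhere, and successfully treated in a low-prevalence area. Some of those patients will have had a false-positive first QFT; the documents do not allow their number to be estimated. No endpoint, alpha allocation, power calculation or analysis changes.
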